13.2.2. Standard calculations

The following calculations will be used:

- Baseline: Last non-missing value on/before randomization date.
- Age=int ((date of ulcer at baseline – birth date + 1) / 365.25).
- Height (cm)
- Weight (kg)
- BMI (kg/m²)
- Clinical Trail Duration:
 - For subjects completing the study: (Four Week Follow-up visit date)-(randomization date)+1
 - For subject withdrawals: (date of withdrawal)-(randomization date)+1
- AE date: (date of onset)-(randomization date)+1
- AE duration: (date of onset)-(randomization date)+1
- Days to complete wound closure: This metric will only be calculated for subjects who achieve investigator-assessed complete wound closure:
 - (Date of the first of two successive 100% epithelialization assessment) – (randomization date) +1
- Days to complete wound closure, as assessed by computerized planimetry: The metric will only be calculated for subjects who achieve planimetric-based complete wound closure during the Treatment Phase. Time to first healing will be used for the analysis

- (Date of the first of two successive planimetric readings of 0cm²) – (randomization date) +1
- Rate of wound closure

Rate (% healed/week) = $7 * [(\text{Baseline wound size}) - (\text{Post-baseline wound size})] / [(\text{Baseline wound size}) * (\text{days in trial})]$

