## 5.15. Adverse Events

### 5.15.1. Definitions

An adverse event (AE) is defined as any untoward medical occurrence occurring in a clinical trial. An AE does not necessarily have a causal relationship with the device. A device-related AE can be any unfavorable and unintended sign, symptom, or disease temporally associated with the use of a study device, whether or not related to the device.

**For the purposes of this study, only AEs that are possibly, probably, or definitely related to the study ulcer, study treatment, and/or study procedures are to be recorded.** All events starting or worsening beginning at SV2 through Treatment Visit Week 13 and unscheduled visits will be collected. Follow-up treatment and evaluation should continue until the AE has resolved or until 2 weeks after the final visit, whichever occurs first.

AEs not related or unlikely related to the study treatment, study ulcer and/or study procedures are not to be recorded for this study.

A Serious Adverse Event (SAE) is defined as any AE that:

- Results in death

- Is life threatening (the subject is at immediate risk of dying from the adverse experience)
- Requires subject hospitalization or prolongs existing hospitalization
- Results in persistent or significant disability/incapacity
- Is a congenital anomaly/birth defect
- Important medical events that may not result in death, be life-threatening, or require hospitalization may be considered a serious adverse device effect when, based upon appropriate medical judgment, they may jeopardize the subject or subject and may require medical or surgical intervention to prevent one of the outcomes listed in this definition.

For the purposes of this study, only SAEs that are possibly, probably, or definitely related to the study ulcer, study treatment, and/or study procedures are to be recorded. All events starting or worsening after the first randomized treatment through Treatment Visit Week 12 will be collected. Follow-up treatment and evaluation should continue until the SAE has resolved or until 2 weeks after the final visit, whichever occurs first.

SAEs not related or unlikely related to the study treatment, study ulcer and/or study procedures are not to be recorded for this study.

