#### 5.15.5. Adverse Event Reporting Procedures

All AEs related to study treatment, study ulcer and/or study procedures spontaneously reported by the subject and/or in response to an open question from study personnel or revealed by observation, physical examination or other diagnostic procedures will be evaluated.

At each visit, after the subject has had the opportunity to spontaneously mention any problems, the investigator should inquire about AEs by asking standard questions such as:

- “Have you had any (other) medical problems since your last visit / assessment?”
- “Have you taken any new medicines since your last visit /assessment?”

The following AEs will be recorded on the appropriate eCRF:

- All AEs related to study treatment, study ulcer and/or study procedures occurring after the 1st randomization treatment.

- All SAEs occurring after signing of ICF through the last study visit

When possible, signs and symptoms indicating a common underlying pathology should be noted as one comprehensive event.

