12. DESCRIPTION OF OTHER VARIABLES AND ANALYSES

12.1. General Statistical Considerations

All collected study data will be presented in subject data listings. Statistical analyses will be performed using SAS® for Windows, version 9.2 or later. Descriptive statistics (n, mean, standard deviation, median, minimum and maximum) will be calculated by treatment group for continuous variables. Frequencies and percentages will be presented by treatment group for categorical variables.

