12.7. Adverse Events

Adverse Events will be coded using the MedDRA Medical Dictionary. AE's are defined as events with an onset after screening visit 1. Treatment Emergent AE's (TEAE) are defined as events with an onset on or after the randomized treatment. TEAEs will be summarized by treatment group, System Organ Class, and preferred term. The following TEAE summaries will be provided:

- TEAEs by severity grade
- TEAEs by relationship to study treatment.

In addition, separate summaries of Serious Adverse Events, and Adverse Events resulting in discontinuation of study treatment will be presented.

The safety population will be used for the safety analyses. Subjects will be counted only once for subject-based analysis. If the same event changes in severity for a subject, the worst severity will be reported.

An Adverse Event is considered treatment emergent if (1) it was not present at Screening Visit 1, and it is not a chronic condition that is part of the subject's medical history; or (2) it is present at Screening Visit 1 or as part of the subject's medical history, but the severity or frequency increases during treatment.

Treatment-emergent adverse events (TEAE) will be summarized for each treatment group by body system and preferred term. The severity of all adverse events will be determined by the investigator's judgment and classified as mild, moderate or severe.

Treatment groups will be compared with respect to the incidence of Adverse Events (all and TEAEs) and the proportion of subjects withdrawing from the study for Adverse Events by reason of withdrawal. Comparisons will be made overall, by body system and by preferred term and will be further categorized by severity and by study device relationship.

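### SAP 13.2.2 gives AE duration the same formula as AE date; with no end date in it, the line returns the day of onset, not the length of the event

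*SAP*

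**What the plan says.** SAP 13.2.2 is a list of derivations that the SAP says will be applied. Two adjacent lines concern adverse events:

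- "AE date: (date of onset)-(randomization date)+1"
- "AE duration: (date of onset)-(randomization date)+1"

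Neither document gives another formula for AE duration. The version 1.1 change history, which was issued to correct errors and edits AE wording elsewhere, does not touch this line.

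On which events are in scope, the documents differ:

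- SAP 12.7: "AE's are defined as events with an onset after screening visit 1".
- Protocol 5.15.1, for AEs: "All events starting or worsening beginning at SV2 through Treatment Visit Week 13 and unscheduled visits will be collected". The same section starts SAE collection only after the first randomized treatment.
- Protocol 5.15.5, for AEs: "All AEs related to study treatment, study ulcer and/or study procedures occurring after the 1", where the sentence goes on to name the first treatment after randomization. For SAEs: "All SAEs occurring after signing of ICF through the last study visit".

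On how long events are followed, Protocol 5.15.1 says: "Follow-up treatment and evaluation should continue until the AE has resolved or until 2 weeks after the final visit, whichever occurs first". Protocol 5.15.6 words it differently. There, AEs are followed until they resolve or stabilize, and a 14-day limit after the final visit applies to SAEs unresolved at the last treatment visit.

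**The concern.** The expression measures how long after randomization an event began. It is the usual formula for study day and is right for that purpose. A duration needs a start and an end, and this formula uses only the start, so two events that begin on the same day get the same value whether they last one day or two months.

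Because the SAP commits to these derivations, a programmer who follows it literally would create a duration variable that duplicates the onset day. Where that variable is shown, a brief late event would look long and a prolonged early one short. Onsets in the screening period would get values that no duration can take.

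**Working it through.** **Inputs.** The formula comes from SAP 13.2.2. Nominal visit days come from the schedule of events: randomization is day 0 and SV2 is day -7 ± 3. The onset and end days below are assumptions for illustration. The documents state no numerical AE duration, so there is no figure of the plan's own to reproduce.

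**Formulas.** With randomization on day 0:

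- SAP duration = onset - 0 + 1
- Elapsed length, counting both end days = end - onset + 1

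**Results.**

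| Onset day | End day | SAP duration | Elapsed length |
|---|---|---|---|
| 60 | 61 | 60 + 1 = 61 | 61 - 60 + 1 = 2 |
| 1 | 40 | 1 + 1 = 2 | 40 - 1 + 1 = 40 |
| 30 | 36 | 30 + 1 = 31 | 36 - 30 + 1 = 7 |
| 6 | 12 | 6 + 1 = 7 | 12 - 6 + 1 = 7 |
| -1 | 3 | -1 + 1 = 0 | 3 - (-1) + 1 = 5 |
| -7 | -3 | -7 + 1 = -6 | -3 - (-7) + 1 = 5 |

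**When the two agree.** They are equal only when end - onset = onset - randomization, that is, when the event lasts exactly as long after its onset as the onset lies after randomization. The fourth row is such a case. On an illustrative grid of onset days -10 to 87 (98 values) and lengths 1 to 60 days, there are 98 × 60 = 5,880 combinations. Agreement needs length = onset + 1, which happens once for each onset day from 0 to 59, so 60 times: 60 / 5,880 = 1.0%. This is the share of grid cells, not a forecast for the trial, since real onsets and lengths are not spread evenly.

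**Whether onsets before randomization occur in the data.** Under SAP 12.7 (after SV1) and Protocol 5.15.1 (from SV2), they are in scope for AEs. Protocol 5.15.5 excludes them for non-serious AEs but includes them for SAEs from consent, whereas Protocol 5.15.1 starts SAEs after the first randomized treatment. Zero and negative values are therefore possible, but how many arise depends on which window is applied.

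**Where a duration could appear.** The safety endpoints and analyses (SAP 3.4, 12.6, 12.7 and the safety paragraph of 13.2.3; Protocol 8.2.4, 8.12.4 and 8.12.5) cover incidence, severity, relationship, SAEs and withdrawals or discontinuations. None names duration. SAP 12.1 says: "All collected study data will be presented in subject data listings". Duration is derived rather than collected, so it may appear in an AE listing, but no section says that it will.

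**The case against.** The strongest reply is that nothing depends on this line. No endpoint, summary or test uses AE duration, and the comparisons in SAP 12.7 are of incidence and withdrawals. The duplicate looks like a copying slip that a programmer would probably notice. That stands as a limit on the consequence. It does not make the line correct: the SAP states it as a rule, and the version 1.1 corrections left it in place.

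Three stronger readings are tempting, and the documents do not support them.

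- A reader might infer that every reported duration will be wrong. The plan does not say that durations will be reported, and the formula can match the true length by chance. What holds is that the formula never measures duration.
- A reader might infer that a difference between arms in time of onset will be presented as a difference in duration. No comparison of durations by arm is planned, so this could happen only if someone added such a table.
- A reader might infer that AE end dates are certainly on file. The follow-up rules imply it, but neither document lists the AE form's fields. By contrast, Protocol 5.14 explicitly lists a stop date for medications. An end date is a reasonable expectation, not a documented fact.

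**Conclusion.** The line is wrong as written. The AE duration formula in SAP 13.2.2 is the study-day formula and cannot measure duration. For a single event the error can be large in either direction: 61 instead of 2 days, or 2 instead of 40, under the assumed dates. Onsets before randomization give zero or negative values, to the extent that the conflicting collection windows let such events into the data.

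The reach is small. It covers the derived variable and any listing or table that displays it. Efficacy results and AE incidence do not change. The duplication itself rests on the text alone. The sizes rest on illustrative dates, and the occurrence of impossible values rests on how the collection windows are applied.

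**What to change.** Replace the line in SAP 13.2.2 with:

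*AE duration: (AE end date) - (date of onset) + 1. For events without an end date, use the date of last AE follow-up and flag the event as ongoing.*

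Keep the present expression for study day of onset only. If AE end dates are not recorded, or duration will not be reported, delete the duration line instead.

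Separately, reconcile the AE and SAE collection windows in Protocol 5.15.1, Protocol 5.15.5 and SAP 12.7, since they decide which onsets before randomization are in the data.

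The formula change costs one line of SAP text and one of programming. It needs no new data if end dates are already collected, which should be checked against the AE form first.

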	
Secondary Efficacy Analyses
 
Proportion of ulcers with complete wound closure during the treatment phase as assessed by computerized planimetry will be compared using Logistic Regression with the stratification factors in the model.
 
Time to complete wound closure will be analyzed using log rank test or Cox proportional regression model. Kaplan-Meier methods will be used to present median time to complete wound closure.
 
Analysis of Covariance will be used to compare the rate of wound closure for the two treatment groups.
 
Safety Analyses
 
AEs related to the device, study ulcer and/or study procedures and all SAEs will be recorded.
 
All safety parameters will be summarized descriptively by treatment assignment. No inferential statistics are planned.
 
Exploratory Analyses
 
Exploratory analyses will be performed to examine patterns of medical resource utilization by treatment group and to estimate the diabetic foot ulcer related treatment costs by treatment. Additionally, wound closure status at the 4-week Follow-up visit will be evaluated.
 
Early Data Review
 
An early data review will be performed when 50 patients reach the primary endpoint. The purpose of this review is to ensure the study execution is as originally planned, and therefore, no alpha spending is involved.
 
Interim Analysis
 
A single interim analysis will be performed when 50% of subjects complete the study. Employing a group-sequential design with a Pocock alpha spending function, the following decisions will be made at the interim analysis with respect to the efficacy outcome:
 
 
• Stop the study due to demonstrating statistically significant superiority of the Active Treatment to SOC if the two-sided p-value testing the stated hypotheses is <math>\leq 0.031</math> and the difference is in favor of the Active Treatment.
 
• Stop the study due to demonstrating futility of the Active Treatment to SOC if the two-sided p-value testing the stated hypotheses is <math>\leq 0.031</math> and the difference is in favor of SOC.
 

--	---

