6. SAMPLE SIZE DETERMINATION AND RATIONALE

This is a randomized study with two treatment groups. Assuming:

- 46% of DFUs receiving PriMatrix close by 12 weeks (84 days).
- 26% of DFUs receiving with Standard of Care close by 12 weeks (84 days).

Overall 2-sided Type I Error rate (alpha) of 0.05. Under the above assumptions, 102 subjects per treatment group will be required to meet the Type I error rate of 0.05 and 80% power; for a total

of 204 subjects for the study. As the treatment duration is short, the discontinuation rate is predicted to be around 15%. To accommodate the potential discontinuations, 240 subjects will be randomized (120 per treatment group) to this trial. The subjects will be randomized to the treatment groups in a 1:1 ratio.

A single interim analysis when 50% of subjects complete the trial, using group-sequential methods and Pocock alpha spending function, where the hypotheses will be tested at a two-sided alpha of 0.031 at the interim analysis and at a two-sided alpha of 0.028 at the final analysis.

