11.2. Secondary Endpoint Analysis

To maintain the trial-wise Type I error rate at 0.05, a closed test procedure will be used for the secondary endpoints. For efficacy analyses, the first date of assessment of 100% re-epithelialization of the wound surface without detectable exudate or visible non-epidermal tissue will be used.

The order of the endpoints to be assessed will be as follows:

- Proportion of subjects with confirmed complete wound closure of the study ulcer during the 12-week Treatment Phase as assessed by computerized planimetry, during the Treatment Phase

A point estimate will be presented along with the exact 95% confidence interval based on the binomial distribution.

- Time to complete wound closure, as assessed by the Investigator.

The endpoint will be summarized by descriptive statistics. In addition, duration of time to complete wound closure/healed will be analyzed as a time-to-event endpoint. The survival curves will be estimated using the Kaplan-Meier method and compared using the log-rank test.

The derivations of time to complete wound closure/healed will be listed for each patient.

- Time to complete wound closure, as assessed by computerized planimetry.

The endpoint will be summarized by descriptive statistics. In addition, duration of time to complete wound closure/healed will also be analyzed as a time-to-event endpoint. The survival curves will be estimated using Kaplan-Meier method and compared using the log-rank test.

The derivations of time to complete wound closure will be listed for each patient.

- Rate of complete wound closure as assessed by computerized planimetry

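### SAP 13.2.2 derives time to closure only for subjects who close and gives non-closers no time or censoring date, which conflicts with the Kaplan-Meier and log-rank analyses planned in 11.2 and 13.2.3

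*SAP*

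**What the plan says.** Time to complete closure is a secondary endpoint twice, by investigator and by planimetry. These are second and third in the ordered closed test of SAP 11.2.

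- **Derivation (SAP 13.2.2).** For the investigator version: "This metric will only be calculated for subjects who achieve investigator-assessed complete wound closure". For planimetry: "The metric will only be calculated for subjects who achieve planimetric-based complete wound closure during the Treatment Phase". The planimetry item adds that the time to first healing is what the analysis will use. Both count from randomization with one day added.
- **Analysis (SAP 11.2 and 13.2.3).** Descriptive statistics come first. Then: "In addition, duration of time to complete wound closure/healed will be analyzed as a time-to-event endpoint". Kaplan-Meier curves are compared by a log-rank test, which 13.2.3 stratifies by ulcer size. SAP 11 places all secondary endpoints in the PEP.
- **Non-closers (SAP 11.6).** Subjects who discontinue before closure are failures for the primary and the secondary endpoints. This is not turned into a time or a censoring rule.
- **Summary measure.** The protocol synopsis says: "Kaplan-Meier methods will be used to present median time to complete wound closure". SAP 12.1 includes the median among the general descriptive statistics.

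**The concern.** A time-to-event analysis needs two variables for each subject: a time and an indicator of whether the event occurred. The SAP derives a time for closers only and never mentions an indicator or a censoring date. A programmer who builds the dataset from 13.2.2 has a missing time for every non-closer, and a missing time drops out of the log-rank test. The comparison would then be between two subsets selected on the outcome, leaving out the subjects in whom the planned treatment difference mostly shows.

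A programmer who instead follows the intent of 11.2 has to invent the censoring rule in an open-label trial. Because the tests are ordered, a failure at the investigator-assessed time endpoint would also block the planimetry time endpoint and the rate of closure.

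The summaries have a related weakness. The planned closure rates are both below one half, so a median may not exist within follow-up. The median most readily available would then be the one among closers.

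**Working it through.** **1. The planning figures reproduce.** SAP 6 states that "102 subjects per treatment group will be required to meet the Type I error rate of 0.05 and 80% power", for closure of 46% against 26% with two looks at two-sided 0.031 and 0.028. With pooled proportion 0.36 and 102 per arm:
- SE = √(2 × 0.36 × 0.64 / 102) = 0.0672, so the standardised effect is 0.20 / 0.0672 = 2.976.
- At half the information the mean of Z is 2.976 × √0.5 = 2.104, and the 0.031 boundary is 2.157.
- P(early stop for superiority) = 1 − Φ(2.157 − 2.104) = 0.479, the SAP's own figure. Overall power is 0.803.

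The rates of 46% and 26% are therefore the right planning inputs. The documents give no figure for time to closure.

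**2. Who would be dropped on the literal reading.** SAP 11.1.1 puts 207 subjects in the PEP; take 104 and 103. Expected closers are 104 × 0.46 ≈ 48 and 103 × 0.26 ≈ 27, together 75. The other 207 − 75 = 132 would have no time value.

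**3. Effect on the log-rank test.** Simulation settings:
- Closure times follow S(t) = exp{ln(1 − p)(t/12)^k}, with t in weeks, p = 0.46 or 0.26, and shape k = 1, 1.5 or 2.
- Times are rounded up to the weekly visit. There is no dropout and no stratification.
- 4,000 trials per shape, with Z = Σ(O − E)/√ΣV over visits, at two-sided 0.05.

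| | k = 1 | k = 1.5 | k = 2 |
|---|---|---|---|
| All subjects, non-closers censored at week 12: significant for PriMatrix | 86.2% | 85.9% | 86.6% |
| Closers only: significant for PriMatrix | 5.2% | 5.0% | 4.8% |
| Mean of closers' medians, weeks (active / control) | 5.6 / 6.1 | 7.3 / 7.6 | 8.3 / 8.6 |

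An independent repeat with 3,000 trials per shape gave 86.0/86.6/85.2% and 5.5/4.9/4.9%. Among closers only, the estimate points towards control in about 36–37% of trials, but significantly so in only 1.0–1.6%.

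**4. The median.** Planned closure at day 84 is 0.46 and 0.26. Both are below 0.50, so neither true median lies within the 12 weeks, whatever the hazard shape. For scale, under an assumed constant hazard:
- Hazard ratio = ln(0.54)/ln(0.74) = 2.05.
- Medians = 84 × ln 2 / −ln(1 − p) = 94 and 193 days.
- Medians among closers = 84 × ln(1 − p/2)/ln(1 − p) = 36 and 39 days. A hazard ratio of about 2 shows up as a three-day difference.

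The observed active-arm curve can still reach 50% by chance. The exact binomial probability is 20.7% with 103 subjects and 23.5% with 104, and across the calculations it is about 21–25%. For control it is practically zero.

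If the 46% already counts 15% dropouts as failures, and dropout is spread evenly and censored when it happens, active closure on the curve is about 49% and it crosses 50% in about 43% of trials. Only if all dropout fell on day 0 would it reach 0.46/0.85 = 54%. Control stays at or below 31%.

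**5. The horizon.** TV13 is at 84 ± 3 days. With the added day in 13.2.2, an on-schedule TV13 closure is day 84 + 1 = 85, and the window runs from 84 − 3 + 1 = 82 to 84 + 3 + 1 = 88.

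**The case against.** A reader might infer that the two time endpoints, as written, compare speed of healing among healers. The strongest reply is that 13.2.2 defines a number, not an analysis population. Days to closure can exist only for someone who closed. Several provisions point towards keeping everyone:
- SAP 11 uses the PEP for all secondary endpoints.
- SAP 11.2 and 13.2.3 name a time-to-event analysis, which by convention keeps subjects without the event as censored observations.
- SAP 11.6 classes discontinued subjects as failures for the secondary endpoints, which makes sense only if they are in those analyses.
- SAP 11.2 says the derivation will be listed for each patient.

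This reply stands as far as it goes. The documents do not establish a closers-only log-rank test, so the loss of power is conditional.

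It does not supply the missing rule. The planimetry item ties the restricted variable to the analysis. The other duration in 13.2.2 cannot serve as a censoring time either. For completers it runs to the four-week follow-up visit, which only subjects with confirmed closure attend.

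Three further replies also hold in part:
- The simulation tests at 0.05. The SAP's level for the final analysis is 0.028, and the documents do not say plainly which applies to the secondary endpoints. At 0.028 both powers would be lower, but the contrast would remain.
- The Kaplan-Meier median is promised only in the protocol synopsis, and a median that is not reached can properly be reported as such.
- Closure may exceed plan: Protocol 1.2 cites 64% in a single-arm study.

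**Conclusion.** The point holds as a derivation rule that conflicts with the planned analysis, together with a missing censoring rule. It does not hold as proof that two controlled secondary endpoints are invalid, or that a real benefit would be missed. If non-closers are censored, power is about 86% and nothing is lost. If 13.2.2 is programmed literally, it is about 5%. These figures rest on 46% against 26% closure, Weibull shapes 1 to 2, no dropout, an unstratified test and two-sided 0.05.

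One part does not depend on the reading: the descriptive statistics for time to closure cover closers only. The median is a poor summary at the planned rates, not an error, and the comparison of 46% and 26% with 50% needs no hazard assumption. The primary analysis is unaffected. The SAP should be corrected before database lock, because the rule left to the programmer decides the outcome of an ordered test.

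**What to change.** In SAP 13.2.2, define a time and an event indicator for every PEP subject, for both the investigator and the planimetry assessment:
- **Closers:** event at the first assessment of a closure that is later confirmed.
- **Completers without confirmed closure:** censored at their last closure assessment in the treatment phase.
- **Discontinued before closure:** carried as not closed to the end of the treatment phase, consistent with 11.6.

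Set that horizon to include the TV13 window under the added-day count, up to day 88. A horizon of day 84 would cut off on-schedule TV13 closures, which fall on day 85.

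Label any summary among closers as descriptive. Report Kaplan-Meier percent closed at Week 12/TV13 alongside the median, with the median given as not reached where that applies. Restricted mean time is optional.

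The cost is SAP wording and a few lines of programming, with no new data. The one drawback is that reported times will look longer than the closers-only figures.

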#### 5.18. Investigator Assessments of Ulcer Closure

**Complete wound closure** is defined as 100% re-epithelialization of the ulcer surface without detectable exudate, confirmed on 2 consecutive study visits 1 week apart (i.e., Treatment Visit where 100% re-epithelialization of the ulcer surface without detectable exudate was initially documented and the Closure Confirmation Visit). For efficacy analyses, the first date of assessment of 100% re-epithelialization of the ulcer surface without detectable exudate will be used as the date of closure.

If, at Treatment Week 12, the ulcer remains open, the investigator will document why, in his opinion, the ulcer did not close.

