3.1. Primary Efficacy Endpoint

The primary efficacy endpoint for the study is the incidence of complete wound closure of the study ulcer, as assessed by the investigator, during the 12-week treatment phase, and confirm one week later.

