12.4. Ulcer Assessment

Data for below questions will be summarized by visit using descriptive statistics

- Ulcer Exudate Assessment
- Ulcer Infection Assessment
- Was picture of the study ulcer taken prior to debridement per protocol
- Ulcer Area
- Ulcer Size Reduction
- Is the Ulcer wound surface 100% re-epithelialized?
- Is the Ulcer wound surface without detectable exudate?
- Is the Ulcer wound surface without visible non-epidermal tissue?
- Extent of Ulceration
- Location of Study Ulcer
- Exudate Type
- Exudate Amount
- Ulcer Infection Assessment

- Ulcer Photography: Pre-Debridement
- Ulcer Measurement: Pre-Debridement.

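### SAP 11.2 and 13.2.2 date investigator-assessed closure by different rules, and neither matches the closure definition in protocol 5.18

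*SAP*

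**What the plan says.** Protocol 5.18 defines complete wound closure as "100% re-epithelialization of the ulcer surface without detectable exudate, confirmed on 2 consecutive study visits 1 week apart", and the SAP's list of abbreviations repeats that definition. Protocol 5.18 also fixes the closure date that efficacy analyses must use: "the first date of assessment of 100% re-epithelialization of the ulcer surface without detectable exudate will be used as the date of closure". The primary endpoint in SAP 3.1 is closure "as assessed by the investigator, during the 12-week treatment phase, and confirm one week later".

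Two other date rules apply to the secondary endpoints:

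- SAP 11.2 says that "the first date of assessment of 100% re-epithelialization of the wound surface without detectable exudate or visible non-epidermal tissue will be used". The secondary-endpoint paragraph of protocol 8.12.1 has nearly the same sentence.
- SAP 13.2.2 computes days to closure from "Date of the first of two successive 100% epithelialization assessment", minus the randomization date, plus 1. It opens with a restriction: "This metric will only be calculated for subjects who achieve investigator-assessed complete wound closure".

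SAP 12.4 lists re-epithelialization, exudate and tissue as separate questions to be summarized by visit. The last of these reads "Is the Ulcer wound surface without visible non-epidermal tissue".

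**The concern.** Time to investigator-assessed closure is the second endpoint in the ordered closed test procedure (SAP 11.2, protocol 8.12.1). Its log-rank result therefore also decides whether the third and fourth endpoints are tested. The log-rank test and the Kaplan-Meier medians depend directly on the event dates.

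With three date rules in the documents, two analysts following them faithfully could derive different dates from the same visit records. The trial is open-label, so choosing between the rules once data are in hand would invite criticism that is easily avoided.

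**Working it through.** The plan gives no figure on this point to reproduce. The check sets the rules side by side and then applies each one to constructed visit sequences.

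**Step 1. Conditions named in each rule**

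| Source | Fully re-epithelialized | No exudate | No non-epidermal tissue | Two visits |
|---|---|---|---|---|
| Protocol 5.18; SAP abbreviations | yes | yes | not named | yes |
| SAP 11.2; protocol 8.12.1, secondary paragraph | yes | yes | yes | not in the sentence |
| SAP 13.2.2, date line | yes | not named | not named | yes |

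The last two rows differ from each other, and neither equals the first. The tissue wording is hard to read as shorthand, because the primary paragraph of protocol 8.12.1 gives the date rule without it and the secondary paragraph of the same section gives it with it.

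**Step 2. Event status under SAP 13.2.2**

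The metric is computed only for subjects with investigator-assessed complete wound closure, a defined term that includes no exudate and confirmation. Every such subject has two successive fully epithelialized visits, so a date always exists. A subject without confirmed closure gets no date. Who has an event is therefore the same as for the primary endpoint, and only the date can move. It can only move earlier, because 13.2.2 asks for less than 5.18.

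**Step 3. Dates under each rule**

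Day = visit date − randomization date + 1 (SAP 13.2.2). The sequences are assumed, at nominal weekly visits, and are not trial data.

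| Sequence (days after randomization) | 5.18 | SAP 11.2 | SAP 13.2.2 |
|---|---|---|---|
| Closed and dry at 42, confirmed at 49 | 43 | 43 | 43 |
| Epithelialized with exudate at 35, dry at 42, confirmed at 49 | 43 | 43 | 36 |
| Epithelialized with exudate at 28 and 35, dry at 42, confirmed at 49 | 43 | 43 | 29 |
| Epithelialized and dry at 42 with tissue recorded; all clear at 49 | 43 | 50 | 43 |
| Epithelialized and dry at 42 and 49, tissue recorded at both | 43 | none by the Confirmation Visit | 43 |

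- The rules agree for a simple closure.
- Under 13.2.2 the date is 43 − 36 = 7 days early in the second row and 43 − 29 = 14 days early in the third.
- Under 11.2 the date is 50 − 43 = 7 days late in the fourth row. In the last row a primary success has no qualifying date if the sentence is applied literally.

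**Step 4. Length of one visit step**

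Seven days is nominal. The schedule of events sets TV2 at 7±3 days and TV3 at 14±3 days, both counted from Day 0. The gap can be as short as (14 − 3) − (7 + 3) = 1 day or as long as (14 + 3) − (7 − 3) = 13 days.

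**Step 5. Number of subjects**

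The documents give no frequency for exudate on a fully epithelialized ulcer, or for non-epidermal tissue recorded alongside full re-epithelialization. The number affected and the effect on the log-rank test cannot be computed.

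**The case against.** The best defence is that a controlling rule already exists. Protocol 5.18 sets the closure date for efficacy analyses, and the SAP states that it is based on protocol version 5.0. The endpoint in SAP 11.2 is time to complete wound closure, a defined term, so confirmation carries over even though the date sentence omits it. A fully re-epithelialized surface should show no non-epidermal tissue, so the extra condition is close to redundant. SAP 12.4 is only a list of items for description and does not show that discordant answers occur.

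Much of this stands. It limits the size of the problem and shows which rule was probably meant. It does not remove the problem: the line in 13.2.2 is the one a programmer would code, and coded as written it gives a date that contradicts 5.18. Nor do the documents say which rule prevails.

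A reader might infer two stronger points, and the documents support neither as a general claim:

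- **That subjects could be primary successes without an event in the log-rank test, or the reverse, so that the Kaplan-Meier curves need not agree with the primary closure rates.** Step 2 rules this out under 13.2.2. Under 11.2 an event is lost only where the tissue item blocks every candidate date. An event is added only if the sentence is read without the defined term, for example an ulcer closed at day 84 and open at confirmation (literal date 85).
- **That the omission favours one arm.** Control dressings are changed daily and active dressings weekly (protocol 5.11), and the exudate assessment counts what the dressing has absorbed (5.7.2), so the finding might behave differently by arm. Nothing in the documents shows that it does, or in which direction.

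**Conclusion.** The point holds as an inconsistency in the closure date of one secondary endpoint, and it should be corrected. As written, SAP 13.2.2 dates closure one or more visits too early for an ulcer that is epithelialized with exudate before it is dry and confirmed, without changing who has an event. SAP 11.2 and the secondary paragraph of protocol 8.12.1 add a tissue condition that can delay the date or, read literally, remove an event, probably rarely. The investigator-assessed primary proportion is not affected.

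This rests on two assumptions: that complete wound closure in 13.2.2 carries its defined meaning, and that the three assessment items can be answered differently at one visit. SAP 12.4 allows for the second by listing them separately but does not demonstrate it.

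**What to change.** Use one date rule for investigator-assessed closure in SAP 11.2, SAP 13.2.2 and the secondary-endpoint paragraph of protocol 8.12.1. The date is the first of the two consecutive visits (closure visit and Confirmation Visit) that both show 100% re-epithelialization and no detectable exudate, as in protocol 5.18. Keep the restriction in 13.2.2 to subjects with complete wound closure. Drop non-epidermal tissue from the date rule; it can stay as a descriptive item under SAP 12.4.

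The cost is one sentence in SAP 11.2, one derivation line in SAP 13.2.2 and one sentence in protocol 8.12.1. Both required items are already listed by visit in SAP 12.4, so no new data are needed. If dates have already been derived, a listing of subjects whose date differs between the rules would show the actual size of the problem.
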